2.8.1 Treatment exposure

Treatment dosing will be investigated both descriptively and graphically:

- Table of treatment duration in total (in months) and frequencies of each separate dose
- Time line of each subject's dosing (Parts 1 & 3 and Parts 2 & 3)

For the plots only: Doses collected in the CRF will be remapped to two variables, one for each unit (mg/m² and mg/kg). Indeed, doses were first collected in mg/m² and unit was changed during Part 1 (see section 1.1). If dose as per CRF is not among the planned doses or dose is missing, the remapped dose variables will be missing. If a visit was missed or (remapped) dose was missing then the last non-missing dose will be displayed. The same is applied for plots with dose as background shading.

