5.1.2 Treatment arms

Part 1:

14 patients have been enrolled into Part 1 in order to establish the MTD or determine with certainty that the MTD cannot be reached. All patients will be treated with branaplam with a weekly single dose. No new patients will be enrolled in Part 1.

Table 5-1	Provisional dose levels for Part 1 dose escalation			
Dose level	Provisional weekly dose	Increment from previous doseb		
-2ª	1 mg/m²	67% reduction		
-1 ^a	3 mg/m²	50% reduction		
1	6 mg/m ²	Starting dose		
2	12 mg/m ²	100% increase		
3	24 mg/m ²	100% increase		
4	48 mg/m ²	100% increase		
5*	60 mg/m ²	25% increase		

^a Dose level -1, and -2 may be used if appropriate (e.g. if the **starting dose** level is not well tolerated)

This table is intended as an example for guidance for the dose escalation part only. Intermediate dose levels may be used and some dose levels may be skipped if the dose-escalation rules presented in this protocol are followed. Actual dose levels will be confirmed in writing by Novartis and provided to all participating study sites before treatment of patients in a new cohort.

Part 2:

A total of 25 patients have been enrolled into Part 2 and assigned to either of the two doses, 0.625 mg/kg or 2.5 mg/kg, previously tested in Part 1 to further evaluate safety and tolerability and change over time in infant growth and motor parameters. All patients will be treated with branaplam.

Part 2 dose levels and regimens were decided from the data generated in Part 1. Actual dose levels and regimens will be confirmed in writing by Novartis and provided to all participating study sites before treatment of patients in Part 2.

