5.4.6 Follow up for toxicities

For patients who do not tolerate the protocol-specified dosing schedule due to drug related toxicities, temporary dose interruptions are permitted.

If the patient has experienced evidence of clinical benefit and in the opinion of the investigator it is in the best interest of the patient to remain on study, then following discussion and agreement with the sponsor, the patient may continue on study treatment.

The guidelines in Table 5-5 should be applied. Novartis study team can at all times during the study ask the investigator to discontinue the treatment, also for reasons not specified in the

Table 5-5. For example, in case emerging PK data for an individual patient is showing higher exposure than anticipated, the investigator could be asked by Novartis study team to lower the dose, even if no toxicity has been observed. Any dose modification must be recorded on the Dosage Administration Record CRF.

Novartis

The below guidance for interruption of study treatment is applicable when there is no clear clinical explanation for the toxicity other than possibly due to study treatment. It may not necessarily apply to abnormalities assessed by the Investigator as associated predominantly with the underlying disease or intercurrent illness. Such cases should be discussed with the Novartis medical team.

Table 5-7 Criteria for interruption and re-initiation of branaplam treatment for AE possibly related to study medication

possibly related to study medication	
Worst toxicity CTCAE Grade ^a	7 days post dose administration (including day of administration)
Blood and lymphatic sys	stem disorders
Anaemia	
Grade 1	Maintain dose
Grade 2 or higher	Suspend dose until resolved to Grade ≤ 1 or baseline
	If not resolved after 14 days then discontinue of study treatment
Neutropenia (ANC)	
Grade 1	Maintain dose
Grade 2	Maintain dose
Grade 3 and Grade 4	Suspend dose until resolved to Grade ≤ 1 or baseline
	If not resolved after 14 days then discontinue of study treatment
Febrile neutropenia	
Grade 3	Suspend dose until resolved
	If not resolved after 14 days then permanently discontinue of study treatment
Grade 4	Suspend dose and discontinue of study treatment
Thrombocytopenia	
Grade 1	Maintain dose
Grade 2 or higher	Suspend dose until resolved to Grade ≤1 or baseline
	If not resolved after 21 days , then permanently discontinue of study treatment
Thrombocytosis	

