2.1 Data analysis general information

A statistical vendor (CRO), [REDACTED] to which the statistical analysis is outsourced, will perform all planned analyses, i.e. IAs (Section 2.13) as well as the final analysis after the final database lock. Details of the analyses for Parts 1, 2, and 3 at the upcoming final database lock are outlined in this document.

Data will be analyzed using SAS® version 9.4 (or higher).

Descriptive summary statistics, unless otherwise specified, for continuous variables include number of non-missing observations (n), mean, median, standard deviation (SD), Q1 (25th percentile), Q3 (75th percentile), minimum and maximum, while for categorical variables frequencies and relative percentages will be reported.

Descriptive analyses will be stratified by part as follows:

- For disposition, demographics, baseline characteristics, and medical history, and protocol deviations, by parts (Part 1, Part 2, Part 1 & 2, Part 3)
- For all other summaries and figures: Part 1 & 3, Part 2 & 3, and Total (where applicable)

For analysis summaries, Part 1 will not be stratified by titration dose, while Part 2 will be stratified by the two treatment doses. For patients in Part 3 from Part 2, the fixed dose in Part 2 will be used as a strata; thus transitions from a low dose to a higher dose in Part 3 will not be analysed separately.

Individual graphs, such as spaghetti plots by study part and treatment and panel plots by study part and subject (with actual dose displayed as background shading) relative to time from first dose (in months) will be provided for selected endpoints, as applicable. Individual graphs relative to calendar age (in months) such as growth curve plots of vital signs, etc. will also be presented.

Listings will be provided by study part, cohort and subject.

The following treatment labels will be used for all tables, listings and figures in the order provided here:

- **Part 1:**
LMI070 0.3125 mg/kg, LMI070 0.625 mg/kg, LMI070 1.25 mg/kg, LMI070 2.5 mg/kg,
LMI070 3.125 mg/kg
- **Part 2:**
LMI070 0.625 mg/kg, LMI070 2.5 mg/kg
- **Part 3 (from Part 1):**
LMI070 0.625 mg/kg, LMI070 2.5 mg/kg, LMI070 3.125 mg/kg
- **Part 3 (from Part 2):**
LMI070 0.625 mg/kg, LMI070 2.5 mg/kg

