2.8.4 Laboratory data

Data summaries will be provided in SI units. The summary of laboratory evaluations will be presented for three groups of laboratory tests: Hematology, Chemistry and Urinalysis. On presenting summary statistics, laboratory data will be grouped and displayed in an alphabetical order within each of the three groups.

Descriptive summary statistics (mean, median, standard deviation, Min and Max) of the change from baseline in the laboratory result to each study visit-window by treatment group will be presented for continuous variables. Change from baseline will only be summarized for subjects with both baseline and post baseline values and will be calculated as:

$$\text{change from baseline} = \text{post baseline value} - \text{baseline value}$$

In addition, shift tables will be provided for all parameters to compare a subject's baseline laboratory evaluation relative to the post-baseline values. For the shift tables, the normal local

laboratory ranges will be used to evaluate whether a particular laboratory test value was normal, low, or high relative to whether or not the baseline value was normal, low, or high. These summaries will be presented by laboratory test overall in Parts 1 & 3, additionally by actual treatment group in Parts 2 & 3. Shift table will also be provided for urinalysis results to compare baseline to post-baseline extreme values (negative, +, 2+, 3+, or 4+).

Number of subjects with newly occurring liver enzymes abnormalities will be summarized using the respective criteria. Newly occurring liver enzymes abnormalities are defined in [Section 5.3.2](#).

For both shift tables and newly occurring liver enzymes abnormalities, all applicable post-baseline values (including unscheduled or unplanned visits) will be checked against the respective criteria and the rules for handling multiple laboratory assessments within visit windows will not be applied.

For continuous variables databased as <lower limit, these will be imputed as being half of the lower limit.

The following graphs will be generated for liver enzymes:

- Panel plot of individual subjects for alkaline phosphatase, total bilirubin, ALT and AST with dose as background shading – one panel per subject (Parts 1 & 3 and Parts 2 & 3)
- eDISH scatterplot of Total Bilirubin and ALT on log-log axes (Parts 1 & 3); additionally stratified by treatment group (Parts 2 & 3)

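### The SAP's carry-forward rule for dose in plots draws suspended and off-plan doses as continuous treatment at the previous planned level

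*SAP*

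**What the plan says.** SAP 2.8.1 limits the rule to figures: "For the plots only: Doses collected in the CRF will be remapped to two variables, one for each unit". It then works in two steps.

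- Step one: "If dose as per CRF is not among the planned doses or dose is missing, the remapped dose variables will be missing".
- Step two: "If a visit was missed or (remapped) dose was missing then the last non-missing dose will be displayed".

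It then extends both steps beyond the dosing time lines: "The same is applied for plots with dose as background shading". No maximum duration is given, and there is no separate display for a suspended or off-plan dose.

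The figures concerned are:

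- the dosing time lines (SAP 2.8.1), the HINE total score panels and the feeding and ventilation time lines (SAP 2.7.1), all for Parts 1 & 3 and Parts 2 & 3;
- the liver plots (SAP 2.8.4), "Panel plot of individual subjects for alkaline phosphatase, total bilirubin, ALT and AST with dose as background shading", also for both groupings;
- the CHOP INTEND change-from-baseline panels (SAP 2.7.1), for Parts 1 & 3 only.

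SAP 2.1 describes the shading in individual panel plots as the actual dose, and SAP 2.1.1 defines that as each child's current dose, derived day by day over the whole study.

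**The concern.** Gaps and off-plan amounts are foreseeable here. For drug-related toxicity, Protocol 5.4.6 states that "temporary dose interruptions are permitted". For Part 1, Protocol 5.1.2 says "Intermediate dose levels may be used and some dose levels may be skipped". Appendix 2 of the protocol has caregivers report under- and over-dosing, and Protocol 9.1.5 has treatment errors entered on the CRF.

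The figures carry weight because of how the rest of the analysis is laid out. In the summaries "Part 1 will not be stratified by titration dose", and SAP 2.8 analyses safety in Parts 1 & 3 overall, with the current dose brought in only through graphics. The shaded panels are thus the main planned display that sets dose beside outcome for each child in those parts. Reading within-child dose changes against outcome is not a remote use: the SAP's rationale for the Part 3 dose cites children who did better or worse after a switch.

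If a child's drug is suspended for raised ALT and ALT then falls, the panel would show recovery under continuous dosing. If motor function declines during an interruption, the panel would show decline on full dose.

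**Working it through.** There is no sample size, power or error rate to reproduce. The check is to apply the rule as written and compare the result with the SAP's own description of the shading.

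**Inputs**

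- Planned levels: 0.3125, 0.625, 1.25, 2.5 and 3.125 mg/kg (SAP Table 1-4). Zero appears in no planned-dose table.
- Zero-dose records: SAP 2.4.1 counts a dose as received only if it is recorded and above zero, so the SAP allows for recorded zeros.
- Suspension length: 14 or 21 days before discontinuation, depending on the event; 21 days for Grade 3 AST or ALT (Protocol Table 5-7).
- Dosing interval: weekly.

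**Doses affected per suspension**

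14 / 7 = 2 and 21 / 7 = 3 weekly doses.

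**The rule applied to illustrative weekly sequences** (mg/kg; assumed, not trial data)

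| Recorded | Displayed | Weeks shown wrongly |
|---|---|---|
| 2.5, 2.5, 0, 0, 0, 2.5 | 2.5 throughout | 3 |
| 2.5, 2.5, three missing, 2.5 (confirmed suspension) | 2.5 throughout | 3 |
| 2.5, 5.0, 2.5 | 2.5 throughout | 1 |
| 2.5, 1.9, 2.5 | 2.5 throughout | 1 |
| 2.5, 0.625, 2.5 | as recorded | 0 |
| 2.5, 2.5, then stopped for four weeks | 2.5 throughout | 4 |

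The second row needs no inference about zeros, because SAP 2.8.1 names missed visits and missing doses as cases to be carried forward. The fifth row shows that an error matching another planned level is displayed correctly.

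**After a permanent stop**

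SAP 2.8.1 does not say when shading ends. The safety cutoff in SAP 2.1.1 includes 30 days after permanent discontinuation, which bounds the liver panels. The efficacy cutoff has no discontinuation term, so the motor panels have no such bound while the child remains in the study.

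**Comparison within the SAP**

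Under 2.1 and 2.1.1 the shading should be the current dose on each day. Under 2.8.1 it is the most recent planned level on record. The two agree only while every dose is recorded and is a planned level.

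**What other outputs keep**

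For 26 weekly doses of which three are recorded as zero, the last dosing day is 26 × 7 − 6 = 176. Expected doses are round((176 − 1) / 7) + 1 = 26, and compliance is 23 / 26 = 88.5%. The gap registers there, though it is not placed in time against a laboratory or motor value.

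**The case against.** The strongest reply is that nothing is lost from the report. The rule applies to plots alone. Administrations are listed by subject (SAP 2.4.2), SAP 2.8.1 also tabulates the separate doses, compliance counts only doses above zero, the AE form records temporary interruption as an action taken (Protocol 9.1.1), and when any laboratory value is abnormal all of that child's values for the parameter are listed (SAP 2.8.4). All of this stands. A reader might infer that the rule conceals a positive dechallenge from the study report; the documents support that only for the figures.

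Other tempting inferences also fail:

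- That the protocol's statements about events resolving on treatment rest on these plots. In Protocol 3.8 those statements concern platelet increases and gastrointestinal events, not ALT.
- That every dosing error disappears. Only off-plan amounts do.
- That the SAP explicitly turns zero into missing. It does not mention zero; this follows only because zero is not a planned level.
- That the reported half-lives measure the problem. They describe drug washout, not how much of a figure is wrong.

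It is also fair to say that the largest dose change in Part 1, the reduction to 6 mg/m² and its reversal, was between planned levels and so is shaded correctly. Motor scales are spaced 6 to 7 weeks apart in Parts 1 and 2 and three months apart in Part 3, so many 2 to 3 week gaps will contain no motor score. Against the 190 weeks reported for the Part 1 extension, three weeks is 3 / 190 = 1.6%. This last point carries less weight for laboratory data, since Protocol 7.4.1 requires clinically relevant deviations to be retested, so values inside a liver-related suspension are likely to exist.

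Finally, doses may be given at home (Protocol 5.2.1 and Appendix 2), so a missed visit or blank record does not prove a missed dose. Leaving every such gap unshaded would create false off-drug periods. That objection shapes the fix.

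**Conclusion.** The concern holds for the figures. As written, SAP 2.8.1 draws suspended and off-plan doses as continuing treatment at the previous planned level, without limit, and contradicts the actual-dose description in SAP 2.1 and 2.1.1. A suspension at the Table 5-7 limits would misplace about 2 to 3 weekly doses in that child's panel, in the main planned display of dose against outcome for Parts 1 & 3.

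No table, listing or compliance figure changes. The overall size cannot be given, because the documents do not state how many children had interruptions or off-plan doses. The conclusion rests on reading the two-step rule literally. For recorded zeros it also rests on the inference that zero counts as off-plan; for missed visits and missing doses no inference is needed. The point merits correction before the figures are produced, but it does not undermine any planned estimate.

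**What to change.** In SAP 2.8.1, replace the carry-forward with separate display categories for all dose time lines and dose-shaded plots:

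- *off drug*: recorded zero, suspended, or confirmed not given;
- *dose unknown*: missed visit or blank record with nothing to confirm whether a dose was given;
- *other dose*: a recorded amount that is not a planned level;
- shading to end after the last dose given, at last dose + 6 days, which matches the exposure rule in SAP 2.4.1.

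State in SAP 2.1.1 that the daily actual-dose variable follows the same categories, so that the definition and the figures agree. This is a display change only and leaves dosing and clinical rules untouched.

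The cost is some programming and a check of home-dosing records, including the patient diaries, to sort gaps into confirmed non-dosing and unknown. Some panels will show stretches of unknown dose, which is less tidy but accurate.

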2.8.2 Adverse events (AEs)

An adverse event (AE) is any untoward medical occurrence (i.e., any unfavorable and unintended sign [including abnormal laboratory findings], symptom or disease) in a subject or clinical investigation of a subject after providing written informed consent for participation in the study. That means that a subject can report AEs before having started study drug. For reporting purposes, the main focus will be on treatment emergent adverse events (TEAEs). Treatment emergent AEs are defined as events starting on or after the first dose of study drug that were absent pre-treatment, or events present prior to the first dose but increased in severity after the first dose (based on the MedDRA lower level term (LLT)). TEAEs are included up to the safety cutoff (as defined in [Section 2.1.1](#)). Except for serious TEAEs and death, only TEAEs up to and including safety cutoff (as defined in [Section 2.1.1](#)) will be included in the analyses. For serious TEAEs a modified safety cutoff is used (as defined in [Section 2.1.1](#)). TEAEs will be assigned to Part 3 if the start date is on/after the first visit date of Part 3 (see section 2.1.1). All deaths will be included, regardless of safety cutoff.

AEs will be reported by primary system organ class (SOC) and preferred term (PT) according to the Medical Dictionary for Regulatory Activities (MedDRA). The MedDRA version used for reporting the study will be described in a footnote.

The number and percentage of subjects reporting any TEAEs will be summarized by primary SOC, preferred term, maximum CTCAE grade (individual, as well as Grade 3 and above combined) and treatment group (Parts 2 & 3). Missing CTCAE grade will not be imputed. Separate summaries will be provided for serious TEAEs, drug related TEAEs, TEAEs leading to permanent discontinuation of study drug and most common TEAEs (10% in any group). Furthermore, exposure-adjusted incidences will be reported in an AE overview table, for all AEs in a table by system organ class and preferred term by part, and similarly for serious AEs.

If a subject reported more than one adverse event within the same primary system organ class, the subject will be counted only once with the maximum CTCAE grade at the system organ class level, where applicable.

All AEs will be presented in listings.

The following graphs will be displayed:

- Bar charts of MedDRA system organ classes - crude incidences
- Bar charts of MedDRA preferred terms - crude incidences
- Similar bar charts for serious TEAEs

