In this study, **'last contact with the subject'** will be the end of study visit, unless an SAE occurs. However, to ensure subject safety, every SAE must be reported to Novartis:

- occurring until 30 days after the last study visit, regardless of causality
- occurring after the 30 days period, if a causal relationship to study treatment is suspected

'Nominal visits' Nominal visits are defined as all scheduled visits as per the clinical study protocol including the EOS visits. The definition of nominal visit excludes unscheduled visits.

'Safety cutoff' Unless explicitly otherwise stated (e.g. SAEs and deaths), data up to and including the safety cutoff will be included in the analysis and data beyond this time point for a given subject will be excluded from the safety analysis. The safety cutoff is defined as the minimum of

- the study day the patient leaves study Parts 1, 2*, or 3
- the database cutoff date (the Final Database Lock date)
- 30 days after permanent study drug discontinuation.
- day of first dose of alternate treatment for SMA

'Efficacy cutoff' Unless explicitly otherwise stated, data up to and including the efficacy cutoff will be included in the analysis and data beyond this time point for a given subject will be excluded from the efficacy analysis. The efficacy cutoff is defined as the minimum of

- the study day the patient leaves study Parts 1, 2*, or 3
- the database cutoff date (the Final Database Lock date)
- day of first dose of alternate treatment for SMA

The following rules will be applied to assign data to part 3:

- a. For datasets/endpoints that have planned visit numbers populated (e.g. HINE, CHOP-INTEND, etc.), the visit number included in the IFC dataset under 'Consent for

additional follow-up study phase' which is the first visit of Part 3 (as confirmed by Cmed) will be used:

i.e. assessments with visit numbers that are \geq that IFC visit number will be assigned to Part 3.

b. For datasets/endpoints that do not have planned visit numbers populated (e.g. AEs, Feeding status, etc.), the visit date that corresponds to the above IFC visit number will be used:

i.e. assessment dates that are \geq that IFC visit date will be assigned to Part 3. In particular, AEs or concomitant medication with start date time \geq that IFC visit date will be assigned to Part 3.

In general, data collected at a visit during the Part 3 will be analysed together with the part the subject came from (i.e. 'Parts 1 & 3', 'Parts 2 & 3').

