The safety cutoff applies to safety analyses only. The only exception to this are serious adverse events and deaths. Any SAEs occurring after the 30 days period, where a causal relationship to study treatment is suspected, will be reported. All deaths will be reported irrespective of safety cutoff.

In general, treatment emergent AEs are defined as events starting after the first dose of study drug that were absent pre-treatment, or events present prior to the first dose but increased in severity after the first dose. This assumes the same AE with increased severity is properly entered as a separate record in the database with start date being the date when severity increases and that a second AE with same severity won't be entered before the same AE is resolved.

For any other safety analyses based on post-baseline abnormalities compared to baseline (i.e. ECGs, vital signs, etc.), where either of the results is not available, the '**missing**' category will be included to avoid any abnormalities being overlooked.

When showing values over time, for subjects who prematurely discontinued the study, study completion visit assessments will be displayed as if they had occurred at the next scheduled visit.

The eGFR is calculated using the MDRD formula. $eGFR [mL/min/1.73 m^2] = 175 \times (\text{serum Creatinine [umol/L]/88.4}) - 1.154 \times (\text{age [years]}) - 0.203 \times (0.742 \text{ if female}) \times (1.212 \text{ if African American})$ ([Levey et al. 2007](#)).

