2.4.1 Exposure to study treatment / compliance / time at risk for AE

Duration of treatment exposure in months = (minimum(study day of last non-missing dose (>0) + 6, end of study date, Database cutoff date) - study day of first dose + 1)/30.4375.

Duration of exposure to study drug will be summarized descriptively on the safety set by parts, treatment group and duration category (≥ 1 mos., ≥ 3 mos., ≥ 6 mos., ≥ 9 mos., ≥ 12 mos., ≥ 18 mos., ≥ 24 mos., ≥ 30 mos., ≥ 36 mos., ≥ 42 mos., etc. till no longer any patients).

For each treatment group, the number of patient-years is calculated as (the sum of the number of days of exposure for all patients in the group)/365.25 and will be summarized by baseline age group and gender.

Time at risk for AE is defined as (in months)

- (minimum(study day of permanent study drug discontinuation + 30, study day of end of study part, Database cutoff date, study day of first dose of alternate treatment for SMA) - study day of first dose + 1)/30.4375 (as defined in [Section 2.1.1](#)).

Time at risk for AEs will be summarized in a similar way to duration of exposure to study drug.

Compliance to the study drug administration schedule will be calculated as

- (Number of doses received / number of expected doses up to treatment discontinuation)*100
- Number of doses received = Doses with non-missing dates and a non-missing dose >0
- Number of expected doses = round((study day of last treatment day-1)/7) + 1
- The last treatment date/day is taken from the CMP dataset.
- If number of received doses exceeds the number of planned doses, then compliance = 100% Premature discontinuation from study drug will not be considered non-compliance.

Last treatment day corresponds to the last record of the administration page for parts 1, 2 or 3 with non-missing date for the patient. A dose is received if dose is non-missing and >0.

This rule means that compliance will be measured during the time interval the patient took study drug: premature discontinuation from study drug will not be considered non-compliance. Compliance to study drug administration will be summarized descriptively on SAF by treatment group. In addition, compliance will be summarized with cumulative number and percentage of patients in each compliance category (*i.e.*, $\geq 20\%$, $\geq 30\%$, $\geq 40\%$, $\geq 50\%$, $\geq 60\%$, $\geq 70\%$, $\geq 80\%$, $\geq 90\%$, $\geq 95\%$, $\geq 98\%$, =100%).

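### Serious adverse events can be counted past the end of the person-time they are divided by, so exposure-adjusted serious-event rates come out equal to or higher than they should, mainly for children who stop early or switch therapy

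*SAP*

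**What the plan says.** **Numerator.** SAP 2.8.2 sets the general rule and its exemption: "Except for serious TEAEs and death, only TEAEs up to and including safety cutoff" are analysed. It then adds "For serious TEAEs a modified safety cutoff is used (as defined in" Section 2.1.1. That section sets the ordinary safety cutoff as the earliest of leaving the study part, database cutoff, "30 days after permanent study drug discontinuation", and the first dose of another SMA treatment. It goes on: "The only exception to this are serious adverse events and deaths". Two statements there could serve as the modified cutoff:

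- Under the definition of last contact, SAEs must be reported if "occurring until 30 days after the last study visit, regardless of causality", and later if a causal relationship is suspected.
- In the text on the exception, "Any SAEs occurring after the 30 days period, where a causal relationship to study treatment is suspected, will be reported".

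**Denominator.** SAP 2.8.2 states that "exposure-adjusted incidences will be reported in an AE overview table", in a table by system organ class and preferred term by part, and likewise for serious AEs. It does not say what the counts are divided by. SAP 2.4.1 offers two quantities. Time at risk for AEs runs to the "minimum(study day of permanent study drug discontinuation + 30, study day of end of study part", database cutoff or first alternate SMA treatment, whichever is earliest. Duration of exposure runs to the last dose plus 6 days (or end of study or database cutoff if earlier), and patient-years are built from it. Neither has a version for serious AEs.

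**Timing.** Protocol 8.2 places the End of Study visit 30 days after the last administration.

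**The concern.** A rate needs events and person-time from the same period. Here the serious-event count is released from the cutoff that bounds other adverse events, while no person-time definition is extended to match. An SAE in the gap adds to the numerator and nothing to the denominator, so the error has only one direction. It also grows as treatment time shortens, so a group with more early stoppers, or more switches to another SMA therapy, would show a higher serious-event rate even if the true rate were the same. Safety is the primary objective of Parts 2 and 3, and SAP 2.8 bases its assessment primarily on adverse event frequency, including serious events.

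**Working it through.** The documents give no serious-event rate or stopping times, so there is no stated figure to reproduce. The check compares the counting window with each person-time definition.

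**Set-up.** First dose is on study day 1 and last dose on study day L. Assumptions: permanent discontinuation is dated at the last dose, the End of Study visit is the last visit and falls at L + 30, and the SAE rate is constant.

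- SAE window, wide reading: L + 30 (visit) + 30 = L + 60 days
- Time at risk (SAP 2.4.1): L + 30 days
- Exposure (SAP 2.4.1): L + 6 days
- Excess = window ÷ person-time − 1

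| Last dose (day) | SAE window | Time at risk | Excess | Exposure | Excess |
|---|---|---|---|---|---|
| 85 | 145 | 115 | +26% | 91 | +59% |
| 358 | 418 | 388 | +8% | 364 | +15% |
| 1095 | 1155 | 1125 | +3% | 1101 | +5% |

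In months of treatment (30.4375 days each), against time at risk:

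- 3 months: 30 ÷ (91.3 + 30) = +25%
- 12 months: 30 ÷ (365.25 + 30) = +8%
- 36 months: 30 ÷ (1095.75 + 30) = +3%

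**Visit window.** In Part 3 the End of Study visit may move by 7 days either way, so the gap is 23 to 37 days. At 12 months that gives 23 ÷ 395.25 = +6% to 37 ÷ 395.25 = +9%.

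**Switch of therapy.** If another SMA treatment starts 7 days after the last dose (assumed), time at risk ends at L + 7. The excess is 145 ÷ 92 = +58% at day 85 and 418 ÷ 365 = +15% (1.145) at day 358.

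**First-event rates.** With rate r, the ratio is [1 − exp(−r(L + 60))] ÷ [1 − exp(−r(L + 30))]. For an assumed r of 0.5 to 2 SAEs per year, the excess is +24% to +17% at day 85, +6% to +2% at day 358, and about +1% to 0% at day 1095.

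**Group level.** Assume 25 children, 5 with last dose at day 85 and 20 at day 1095. The window is 5 × 145 + 20 × 1155 = 23,825 days. Time at risk is 5 × 115 + 20 × 1125 = 23,075 days. The ratio is 1.033, about +3%.

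**Narrow reading.** Only suspected-related SAEs are added after the 30-day period, with no stated upper limit. The percentages above do not apply, because the added events are a selected subset over an open-ended time. They still enter with no person-time, so the direction is the same.

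**If exposure is the denominator.** Non-serious events would be mismatched too, since they count to L + 30 against L + 6 days: 115 ÷ 91 = +26% at day 85 and 388 ÷ 364 = +7% at day 358.

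**The case against.** The best defence is that the wide window is an interpretation. The text on 30 days after the last visit is framed as a duty to report SAEs to the sponsor, matching Protocol 9.1.3, and is not labelled an analysis window. The 30-day period in the exception could equally mean 30 days after drug discontinuation. This stands: the percentages belong to the wide reading only. It does not remove the mismatch, because the narrow reading also adds events without person-time.

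A second defence is that the denominator is unnamed, so a mismatch cannot be asserted. Both definitions in SAP 2.4.1 end before the SAE count, so the conclusion does not depend on the choice; its size does.

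Third, the consequence is limited. All parts are non-confirmatory, no test of SAE rates is planned, crude incidences remain, and Part 3 entry requires at least 52 weeks of treatment, so the 3-month figure cannot describe anyone who reached Part 3. All of this stands and limits the weight of the point.

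Three stronger readings are tempting:

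- **Serious events cluster after stopping, so the excess is much larger.** Protocol 8.1.1 lists progression among several reasons to stop, but the documents give no counts and no post-stop rate. If the rate were five times higher from drug stop (an assumption), the excess would be 150 ÷ (91.3 + 150) = +62% at 3 months, 150 ÷ (365.25 + 150) = +29% at 12 and 150 ÷ (1095.75 + 150) = +12% at 36. That is a sensitivity figure, not a finding.
- **All deaths at any time enter the serious-event rate.** SAP 2.8.3 summarises deaths as number and percentage, and Protocol 9.1.1 collects death outside AE grading. Use in the rate is not stated.
- **Dose-group comparisons are biased.** The system organ class and preferred term rate tables are specified by part, so this is only partly supported.

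**Conclusion.** The concern holds in this form. The SAP exempts serious TEAEs from the ordinary cutoff, points to a modified cutoff that Section 2.1.1 does not define by name, and plans a serious-event rate whose possible denominators both stop earlier. The rate is therefore equal to or higher than it should be, never lower. It is actually raised only when a counted SAE falls in the gap. There is no gap for a child who dies on treatment or is still treated at database cutoff.

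The per-child sizes rest on the wide reading, a constant rate, time at risk as denominator, and an End of Study visit held on schedule. Where most children have long follow-up, the excess in a reported group rate may be only a few percent, and less for first-event rates. The point merits correction because it affects a planned primary-objective safety table and is cheap to remove. It does not undermine the safety analysis as a whole.

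**What to change.** Make three changes to the SAP:

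1. In Section 2.1.1, define the modified safety cutoff by name, and state whether the period after the last visit is an analysis window or only a reporting duty.
2. In Section 2.8.2, name the time at risk from Section 2.4.1 as the denominator for all exposure-adjusted incidences. This also keeps non-serious events matched to their person-time.
3. For the exposure-adjusted serious-AE incidence, count only SAEs with onset inside that time at risk.

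SAEs after that point, and all deaths, stay in the crude serious-AE and death tables and are listed separately, so no safety information is lost. Extending person-time instead would not suffice on the narrow reading, because the late events are selected by suspected causality. The cost is a few SAP sentences and one filter in the program.
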